COVID-19 Therapeutics	

Sponsor-designated standard of care for treatment for COVID-19 is permitted (eg, remdesivir, corticosteroids, etc.) but may require additional safety monitoring as determined by the treating clinician.

If guidelines for local standard of care conflict with Sponsor-designated standard of care, site should consult with Sponsor.

Supportive therapies (including but not limited to anti-pyretic and anti-inflammatory agents) to manage COVID-19 signs/symptoms are allowed.

Unless designated by the Sponsor as acceptable standard of care for COVID-19, concomitant use of other therapies intended as specific treatment for COVID-19 are prohibited from randomization through Day 29.

Non-COVID-19 Investigational agents	All non-COVID-19 investigational agents including devices are prohibited within 30 days prior to randomization and through Day 29.

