### **9.5 Analysis Populations**

#### **9.5.1 Efficacy Analysis Populations**

The MITT population will serve as the primary population for the analysis of efficacy data for both parts of this study. The MITT population consists of all randomized participants who received at least 1 dose of study intervention. Part 1 (Phase 2) and Part 2 (Phase 3) of the study will be analyzed separately for efficacy endpoints. Therefore, the MITT population for Part 2 will not include Part 1 participants, and vice versa.

A supportive analysis using the Per-Protocol population will be performed for primary and secondary efficacy endpoint(s) for Part 2. The Per-Protocol population excludes participants due to deviations from the protocol that may substantially affect the results of the primary efficacy endpoint.

The final determination on protocol deviations, and thereby the composition of the Per-Protocol population, will be made prior to the final unblinding of the database and will be documented in a separate memo.

Participants will be included in the treatment group to which they are randomized for the analysis of efficacy data using both the MITT and Per-Protocol populations.

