### 9.6.1 Statistical Methods for Efficacy Analyses

The stratified log-rank test will be used for the comparison of MK-4482 with placebo for the primary endpoint of the time-to-sustained recovery. Stratification factors are specified in Section 6.3.2. The relevant treatment efficacy parameter is the “sustained recovery rate ratio” (for MK-4482 relative to placebo), which is akin to the hazard ratio in survival analysis but for the beneficial outcome of sustained recovery. Sustained recovery rate ratios will be based on the stratified Cox Proportional Hazards regression model with stratification by factors specified in Section 6.3.2. Geographic region will not be used as a covariate in the primary analyses, but it may be considered as an additional stratification factor for the stratified log rank test and as a covariate for the Cox Proportional Hazards regression model for sensitivity analysis if it does not cause sparse data issues. The number of regions along with the specific countries contained within each region will be described in the sSAP. The Efron approximation will be used for handling ties. Failure to recover will be censored at Day 29. Death before Day 29, including death following a prior recovery, will be censored at Day 29 to eliminate any bias that would be introduced by censoring at time of death. Lost to follow-up before Day 29, regardless of prior recovery, will not be considered a sustained recovery and will be censored at the day of last contact. Withdrawal (ie, discontinuation from the study for reasons other than death or lost to follow up) before Day 29, regardless of prior recovery, will not be considered a sustained recovery and will be censored at the day of discontinuation.

Participants who initiate Sponsor-designed standard of care for treatment for COVID-19 48 hours or more following start of randomized study therapy will be treated as a failure to recover. Sustained recovery rate ratios greater than 1 indicate a benefit for MK-4482. Superiority will be concluded based on p-value boundaries as described in Sections 9.7 and 9.8.

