Time-to-sustained recovery from randomization through Day 29	P (MITT) S (PP)	Stratified log-rank test c  Stratified Cox Proportional Hazards regression d	MITT PP	
Missing data will not be imputed.
 
Participants who initiate Sponsor-designated standard of care for treatment for COVID-19 48 hours or more following start of randomized study therapy will be treated as a failure to recover.
 
A sensitivity analysis for the primary efficacy endpoint will be performed in the MITT population that does not impute “failure to recover” for participants who initiate Sponsor-designated standard of care for treatment for COVID-19.
 
Depending upon the number of participants who required re-hospitalization but were discharged or medically ready for discharge again before Day 29, an additional sensitivity analyses will be performed in which all participants with re-hospitalizations by Day 29 are considered as not meeting the primary endpoint.
 
Failure to recover will be censored at Day 29. Death will also be censored at Day 29. Recovery followed by subsequent lost to follow up before Day 29 will be censored at the day of lost to follow up. Withdrawal (ie, discontinuation from the study for reasons other than death or lost to follow up) before Day 29 will be censored at the day of discontinuation.

Endpoint/Variable (Description, Time Point)	Primary vs. Supportive Approach a	Statistical Method b	Analysis Population	Missing Data and Data Imputation Approach
Secondary Endpoints				
All-cause mortality through Day 29	P (MITT) S (PP)	Unstratified M & N method c	MITT PP	Missing = Failure (M=F) – MITT Data as Observed (DAO) - PP
Odds of a more favorable response on Pulmonary score at Day 3, EOT, Day 10, Day 15, and Day 29	P (MITT) S (PP)	Proportional odds model d	MITT PP	Model-based
Odds of a more favorable response on Pulmonary+ score at Day 3, EOT, Day 10, Day 15, and Day 29	P (MITT) S (PP)	Proportional odds model d	MITT PP	Model-based
Odds of a more favorable response in the clinical risk of mortality category from the National Early Warning Score at EOT	P (MITT) S (PP)	Proportional odds model d	MITT PP	Model-based
Odds of a more favorable response on the WHO 11-point ordinal scale on Day 3, EOT, Day 10, Day 15 and Day 29	P (MITT) S (PP)	Proportional odds model d	MITT PP	Model-based

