## 9.8 Multiplicity

Multiplicity adjustment with regard to controlling type I error for the Futility/Early Efficacy (Phase 3) Interim Analysis is described in Section 9.7.

There are two hierarchical superiority hypotheses in the Phase 3 part of this study (Section 3). A sequential testing approach will be employed to control overall type I error at 0.025, 1-sided across the primary efficacy endpoint (time-to-sustained recovery) and the key secondary efficacy endpoint (all-cause mortality). The all-cause mortality endpoint will not be tested at the interim analysis. At the end of Part 2, testing will be performed for the time-to-sustained recovery endpoint at an alpha level of 0.019. If superiority is demonstrated, the all-cause mortality endpoint will be tested at alpha level of 0.025. This strategy provides strong control of type I error at the study level. All tests are 1-sided unless otherwise noted.

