## 9.9 Sample Size and Power Calculations

### 9.9.1 Sample Size and Power Calculations for Efficacy Analyses (Part 2)

The primary analysis of Phase 3 study endpoints will include ~1000 participants from Part 2 of the study (~500 for the selected MK-4482 group and ~500 for the placebo group) who meet the criteria for inclusion in the MITT population. The primary endpoint is time-to-sustained recovery. The study has overall power of 90% to demonstrate that participants treated with MK-4482 have a higher rate of sustained recovery than participants treated with placebo at an overall one-sided, 2.5% alpha-level, if the underlying constant sustained recovery rate ratio between treatment groups is 1.3.

The power and sample size are based on the following assumptions: 1) the time-to-sustained recovery follows an exponential distribution with sustained recovery rates of 0.351 and 0.270 for the MK-4482 and placebo groups, respectively, 2) a futility/efficacy interim analysis at 50% information as outlined in Section 9.7, 3) an enrollment period of 10 weeks, and 4) dropout hazard rates of 0.02 for both the MK-4482 and placebo groups, respectively. The above sustained recovery rates correspond to approximately 366 (73%) and 319 (64%) sustained recovery events for the MK-4482 and placebo groups, respectively. These are nearly identical to the recovery rates presented for remdesivir and placebo in the NEJM [Beigel, J. H., et al 2020]. The calculation was computed using both EAST and gsDesign. To meet the statistical criterion for success (one-sided p value $\leq$ 0.019 at the final analysis), the observed sustained recovery rate ratio must be approximately 1.17 or larger.

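### Late start of Sponsor-designated care is scored as failure to recover, but late start of a prohibited COVID-19 therapy is not, so the same clinical course can count either way in the primary analysis.

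*Combined protocol and SAP*

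**What the plan says.** Section 9.6.1, on the primary endpoint: "Participants who initiate Sponsor-designed standard of care for treatment for COVID-19 48 hours or more following start of randomized study therapy will be treated as" failures to recover, which the same section censors at Day 29. Table 5 gives the rule again with one word changed: "Participants who initiate Sponsor-designated standard of care for treatment for COVID-19 48 hours or more following start of randomized study therapy will be treated as" failures. A sensitivity analysis in the MITT population removes this imputation, again for Sponsor-listed care only.

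Section 6.5, Table 2, divides specific COVID-19 treatments into two classes. Those on the Sponsor's list are permitted. For the rest: "Unless designated by the Sponsor as acceptable standard of care for COVID-19, concomitant use of other therapies intended as specific treatment for COVID-19 are prohibited". That ban lasts until Day 29, starting at randomization. Section 6.5 adds that a clinical need for a prohibited medication may require study intervention to be stopped. Section 7.1 says that stopping study intervention is not withdrawal from the study.

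The definition of sustained recovery (Sections 4.2.1.1.1 and 9.4.1.1) sets no condition on the therapy received. The list of events that do not qualify does not mention concomitant therapy.

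The supportive population is described in Section 9.5.1: "The Per-Protocol population excludes participants due to deviations from the protocol that may substantially affect the results of the primary efficacy endpoint". Prohibited therapy is not named there, and the deviations are to be settled in a memo before final unblinding.

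**The concern.** The failure rule exists so that a discharge reached with the help of late added treatment is not counted as a recovery on the randomized arm. It covers the permitted class and leaves out the prohibited one.

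Take two participants who worsen after 48 hours, receive a specific COVID-19 drug, go home on Day 12 and stay well to Day 29. If the drug is on the Sponsor's list, the participant is a failure censored at Day 29. If it is not, the participant is a recovery on Day 12. The therapy that departs from the protocol is the one that earns credit.

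Late rescue is a response to not improving, so its use may differ by arm. Recoveries that it helps to produce then count for the arm that used it more. Care outside the list may also vary by site, so scoring can depend on where a participant was treated.

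**Working it through.** **1. Does another rule close the gap?**

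| Rule | Effect on late prohibited therapy followed by discharge |
|---|---|
| Failure rule (9.6.1, Table 5) | Not triggered: Sponsor-listed care only |
| Events that are not sustained recovery (9.4.1.1) | Not listed |
| Possible stop of study intervention (6.5) | No endpoint consequence |
| Censoring at withdrawal (9.6.1) | Not triggered: stopping treatment is not withdrawal (7.1) |
| No-imputation sensitivity analysis (9.6.1) | Not addressed |
| Per-Protocol (9.5.1) | May exclude the participant; does not score a failure |

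None does. The primary analysis counts a recovery, Per-Protocol can at most exclude it, and no planned analysis counts a failure.

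**2. The plan's own figures.** Section 9.9.1: "The study has overall power of 90% to demonstrate that participants treated with MK-4482 have a higher rate of sustained recovery", "if the underlying constant sustained recovery rate ratio between treatment groups is 1.3". Inputs are recovery rates 0.351 and 0.270, dropout 0.02, 500 per arm and four weeks of follow-up. The rates reproduce the plan's events when read as weekly.

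Events per arm = 500 × λ/(λ+δ) × [1 − exp(−4(λ+δ))].

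- MK-4482: 500 × (0.351/0.371) × [1 − exp(−1.484)] = 365.8 (plan: 366).
- Placebo: 500 × (0.270/0.290) × [1 − exp(−1.160)] = 319.6 (plan: 319).

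The total is 685, as stated. Section 9.8 says it will "control overall type I error at 0.025, 1-sided across the primary efficacy endpoint" and the key secondary endpoint. Gamma spending with γ = −1 at half information spends 0.025 × (1 − e^0.5)/(1 − e) = 0.0094, so z = 2.348 and the interim ratio boundary is exp(2 × 2.348/√342.5) = 1.289. At the final look z = 2.066 (p = 0.0194), with ratio boundary exp(2 × 2.066/√685) = 1.171. This matches Section 9.8: "testing will be performed for the time-to-sustained recovery endpoint at an alpha level of 0.019". Power is 90.4% if the futility boundary is followed and 91.9% if it is ignored, so the stated 90% reproduces. The stated assumptions make no allowance for late therapy of either class.

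**3. Illustration of size.** The documents give no rate of late prohibited use, so the rates below are assumptions. Simulation: 500 per arm, the rates and dropout above, 3,000 trials per scenario, unstratified log-rank test at one-sided 0.019, final look only. Use is the chance of starting such therapy among those not recovered by Day 3. After it, both arms are assumed to recover at 0.351 per week. *Credited* is the current text. *Failure* applies the rule for listed care.

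| Use, MK-4482 / placebo | Credited: ratio, power | Failure: ratio, power |
|---|---|---|
| none | 1.30, 92% | same |
| 3% / 5% | 1.29, 89% | 1.33, 94% |
| 5% / 10% | 1.28, 86% | 1.38, 97% |
| 10% / 20% | 1.25, 79% | 1.46, >99% |
| 5% / 5% | 1.29, 88% | 1.29, 88% |
| 10% / 10% | 1.27, 86% | 1.28, 84% |
| 10% / 5% | 1.29, 89% | 1.20, 58% |

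**4. No drug effect** (0.270 in both arms), rejection at nominal 0.019:

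| Use, MK-4482 / placebo | Credited | Failure |
|---|---|---|
| 5% / 10% | 1.0% | 10.7% |
| 10% / 5% | 2.7% | 0.1% |

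With equal use and no drug effect the arms are exchangeable, so either rule keeps the nominal level.

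**The case against.** The gap arises from silence. No sentence says that these recoveries count, and leaving protocol violations in MITT as observed is a recognised treatment-policy choice. That is fair, but the plan made the opposite choice for listed care and gives no reason for treating the two classes differently.

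Use should be low. Exclusion criterion 10 bars anyone taking, or expected to need, a prohibited therapy. Criterion 11 bars those unwilling to stay out of other interventional trials through Day 29. Table 2 tells sites to consult the Sponsor when local guidelines conflict with its list. This stands and limits the size, although it sets no scoring rule.

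A reader might infer that the current rule has been shown to bias the result, by setting 1.28 against 1.38 in the 5% / 10% row. The figures do not show that. The simulated drug effect is 1.30; the current rule moves the estimate by about 0.02, and most of the distance to 1.38 is made by the failure rule. If rescue gave no benefit, crediting these recoveries would leave the ratio at 1.30.

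A reader might also infer that the gap favours MK-4482. If placebo uses more, it works against MK-4482. In the reverse case the null rejection rate rises only to about 2.7%.

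The strongest point concerns the remedy. Scoring these participants as failures is not neutral: with no drug effect and 5% / 10% use it rejects about 10.7% of the time, and with a real effect and 10% / 5% use it cuts power from 89% to 58%. Such imbalance is unlikely under blinding with an inert drug. The existing rule for listed care has the same property, and the plan answers it with a no-imputation analysis.

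**Conclusion.** The inconsistency is certain from the text: in the primary MITT analysis, the same course is a failure after late permitted therapy and a success after late prohibited therapy. Its effect on the result is unknown, because no rate of use is given, and it is probably small. At an assumed 3% to 10% use, with a rescue benefit that lifts both arms to 0.351 per week, the ratio falls from 1.30 to about 1.27 to 1.29 and power from 92% to between 86% and 89%. A ratio of 1.25 needs 10% / 20% use of therapies that the protocol forbids. With equal use the two rules differ by less than 0.01 in the ratio.

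The documents support a call to state the handling and make it consistent before unblinding. They do not support a finding that the primary analysis as written is materially biased in either direction.

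**What to change.** - In Section 9.6.1 and Table 5, extend the trigger to any therapy intended as specific treatment for COVID-19, whether Sponsor-designated or prohibited by Table 2, started 48 hours or more after the start of study therapy.
- Extend the existing no-imputation sensitivity analysis to the same set, so that both handlings are reported side by side.
- Report late start of each class of therapy by arm.
- Use one term for the Sponsor's list. Section 9.6.1 says designed where Table 2 and Table 5 say designated, and the failure rule depends on that list.

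Because this changes a method for the primary hypothesis, the opening of Section 9 requires a protocol amendment before unblinding. No new data are needed: Section 8.1.5.2 already has all concomitant COVID-19 therapeutics recorded. What sites may give does not change.

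The cost is somewhat fewer events (about 657 against 688 at 5% use in both arms) and a primary result that is sensitive to unequal use. The paired sensitivity analysis and the counts by arm would show that.

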### **Part 2 (Phase 3 - Evaluation of Selected Dose)**

In Part 2, ~1000 participants will be randomized in a 1:1 ratio (stratified per Section 6.3.2) to receive either the selected dose of MK-4482 or placebo ([Figure 1](#)). An interim efficacy analysis is planned in Part 2 (Section 9.7).

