#### **6.3.2 Stratification**

Intervention randomization will be stratified according to the following factors:

1. Time from symptom onset prior to the day of randomization ( $\leq 5$  days,  $>5$  days)
2. Age ( $\leq 60$  years,  $>60$  years)
3. Remdesivir use for treatment of the index diagnosis of COVID-19 prior to or at the time of randomization (yes, no)

Based on the viral kinetics of SARS-CoV-2 and the mechanism of action of MK-4482, treatment with antiviral therapy is likely to have a greater benefit with early treatment ( $\leq 5$  days) rather than late treatment ( $>5$  days). Older age is also associated with more severe outcomes, and the WHO notes that people older than 60 years are at higher risk for severe illness due to COVID-19. Finally, remdesivir has been demonstrated to shorten the time to recovery in hospitalized patients with COVID-19 and may be used concurrently in this study. The selection of these criteria as stratification factors will help ensure that the treatment groups will be well balanced within each stratum and the study results will not be confounded by factors suspected to have a potential impact on a participant's response to study intervention.

Of note, enrollment of participants with severe COVID-19 (Appendix 9) will be limited to 50% of the total planned sample size in both Parts 1 and 2.

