A sensitivity analyses for the primary efficacy endpoint will be performed in the MITT population that does not impute “failure to recover” for participants who initiate Sponsor-designed standard of care for treatment for COVID-19 following start of randomized study therapy. In the case where the number of participants who require re-hospitalization but are then discharged again (or medically ready for discharge) before Day 29 exceeds 5% of the total MITT population, an additional sensitivity analysis will be performed in which all participants with re-hospitalizations by Day 29 are considered as not meeting the primary endpoint.

If superiority of MK-4482 over placebo is demonstrated as assessed by time-to-sustained recovery at the end of Part 2, the superiority of MK-4482 over placebo as assessed for the key secondary endpoint of all-cause mortality at Day 29 will be tested. Due to the relatively low number of deaths expected and the large number of strata levels, the unstratified Miettinen and Nurminen method [Miettinen, O. 1985] will be used to estimate and test the treatment difference for all-cause mortality. Every effort will be made to ascertain survival status for all participants. Missing data for this endpoint will be treated as failure (M=F approach) in the MITT population.

Ordinal outcome scales such as Pulmonary and Pulmonary+ will be analyzed using the cumulative logits function and the proportional odds model as described by McCullagh [McCullagh, P. 1980]. This methodology provides an estimate of the common odds ratio for assessing differences between treatment groups. In addition to a term for treatment group, the model will include terms for the stratification factors specified in Section 6.3.2. In addition, the proportion of participants in each ordinal scale category by treatment groups will also be presented.

The National Early Warning Score and the WHO 11-point ordinal scale score will be categorized to ordinal outcomes and will be further analyzed using the same approach as for Pulmonary and Pulmonary+ outcomes.

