The viral RNA endpoints at earlier time points (Day 3 and EOT) will be important for the dose selection decision from Part 1 of the study. Change from baseline in SARS-CoV-2 RNA titer, calculated as  $\log_{10}$  (post) minus  $\log_{10}$  (baseline), as measured by quantitative RT-PCR of samples from NP and OP swabs will be summarized separately by treatment group and time point. The DAO approach will be used to handle missing data for these summary statistics. In addition to summary statistics, treatment differences in change in SARS-CoV-2 RNA titer from baseline over time will be estimated using longitudinal models. Graphical presentations of the change from baseline will be presented and the impact of baseline viral RNA level will be explored using subgroup analyses (defined by level of baseline viral RNA) and analyses/summaries that exclude participants with low baseline levels (eg, viral RNA  $<10^6$  copies/mL).

Percentage of participants with undetectable viral RNA (below limit of detection) as measured by qualitative RT-PCR of samples from NP and OP swabs will be summarized separately by treatment group and time point. Between-treatment differences and 95% confidence intervals will be estimated using the stratified Miettinen and Nurminen method [Miettinen, O. 1985].

A detailed analysis strategy for key efficacy endpoints is listed in [Table 5](#). The strategy to address multiplicity issues with regard to multiple efficacy endpoints and interim analyses is described in Section 9.7, Interim Analyses and in Section 9.8, Multiplicity.

Table 5 Analysis Strategy for Key Efficacy Endpoints

Endpoint/Variable (Description, Time Point)	Primary vs. Supportive Approach a	Statistical Method b	Analysis Population	Missing Data and Data Imputation Approach
Primary Endpoint				

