### **Tier 1 Events**

Safety parameters or AEs of special interest that are identified a priori constitute "Tier 1" safety endpoints that will be subject to inferential testing for statistical significance with p-values and 95% CIs to be provided for between-treatment differences in the proportion of participants with events; these analyses will be performed using the unstratified Miettinen and Nurminen method [Miettinen, O. 1985], an unconditional, asymptotic method. Since the stratification factors are not considered to be related to safety endpoints, they will not be included as stratification factors in the safety analyses.

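### Stratifying the Day 29 mortality test (H2) by age group alone would be a small, nearly free gain in precision; the planned unstratified test is valid but slightly conservative if age predicts death

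*Combined protocol and SAP*

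**What the plan says.** Section 6.3.2: "Intervention randomization will be stratified according to the following factors", namely time from symptom onset (≤5, >5 days), age (≤60, >60 years) and remdesivir use (yes, no). That makes 2 × 2 × 2 = 8 cells. On age, the section states: "Older age is also associated with more severe outcomes".

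Section 9.6.1 and the notes to Table 5 carry these factors into the primary stratified log-rank test and Cox model, and into the proportional odds models for the ordinal scales. Mortality is the exception: "Due to the relatively low number of deaths expected and the large number of strata levels, the unstratified Miettinen and Nurminen method" is named for both the test and the estimate, and Table 5 agrees. No age-adjusted mortality analysis is listed, even as a sensitivity analysis.

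Section 9.8 puts H2 under alpha control: "If superiority is demonstrated, the all-cause mortality endpoint will be tested at alpha level of 0.025", and "All tests are 1-sided unless otherwise noted".

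Two other places bear on the choice. For undetectable viral RNA, Section 9.6.1 says: "Between-treatment differences and 95% confidence intervals will be estimated using the stratified Miettinen and Nurminen method". For Tier 1 safety events, Section 9.6.2 drops the strata for a different reason: "Since the stratification factors are not considered to be related to safety endpoints". That reason is not offered for mortality.

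**The concern.** When a prognostic factor is balanced by design, chance imbalance in that factor no longer adds to the variability of the treatment difference. An unstratified variance still includes that component. The standard error is then larger than the true one, the test rejects less often than its nominal level under the null, and the interval is wider than it needs to be.

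H2 is the only confirmatory hypothesis after the primary. The plan gives no power for it and expects few deaths, so precision on mortality is scarce. The stated reason treats the choice as all strata or none. Age alone leaves two strata, and age is the factor whose link with severe outcomes the protocol states outright.

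**Working it through.** **The plan's own figures.** None is given for H2: no mortality rate, power or interval width. The only efficacy power statement for Part 2 concerns the primary endpoint, and it reproduces. With 685 events, a rate ratio of 1.3, one look at 50% information and gamma = −1, the nominal p-values come out at 0.0094 (interim) and 0.0194 (final), against the stated 0.009 and 0.019. Power is 90.4% with the futility bound applied, against the stated 90%. This does not bear on H2, so the size below rests on assumed mortality.

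**Inputs from the documents.** Part 2: about "1000 participants will be randomized in a 1:1 ratio", hence n = 500 per arm. Age strata ≤60 and >60. One-sided alpha 0.025, critical value 1.96.

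**Assumed inputs.** Share aged over 60, s = 40–50%. Day 29 mortality a = 2–4% (≤60) and b = 12–20% (>60). Arms balanced within age group.

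**Formulas.** Overall mortality p = (1−s)a + sb. Variance term used by the unstratified method: V = p(1−p). Part removed by age-stratified randomization: B = s(1−s)(b−a)². Ratio of true to used standard error: r = √(1 − B/V). Actual one-sided alpha = 1 − Φ(1.96/r). Excess interval width = 1/r − 1.

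**Worked example (3%, 12%, s = 40%).** p = 0.6×0.03 + 0.4×0.12 = 0.066. V = 0.066×0.934 = 0.0616. B = 0.24×0.09² = 0.0019. B/V = 0.0315, r = 0.984. Alpha = 1 − Φ(1.992) = 0.0232; the interval is 1.6% too wide. Its half-width 1.96√(2V/500) is 3.08 percentage points, against 3.03 with the correct variance.

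**Five scenarios.** Simulated columns: 200,000 trials each, score test, sample-size weights for the stratified version. Power is at an assumed mortality risk ratio of 0.55.

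| a, b, s | r² | Excess width | Alpha, formula | Alpha, simulated: unstratified / by age | Power: unstratified → by age |
|---|---|---|---|---|---|
| 3%, 12%, 40% | 0.968 | 1.6% | 0.0232 | 0.0228 / 0.0249 | 57.0 → 58.3% |
| 2%, 15%, 40% | 0.939 | 3.2% | 0.0216 | 0.0210 / 0.0246 | 61.5 → 63.6% |
| 3%, 18%, 50% | 0.940 | 3.1% | 0.0216 | 0.0208 / 0.0243 | 79.2 → 80.6% |
| 2%, 20%, 40% | 0.907 | 5.0% | 0.0198 | 0.0197 / 0.0248 | 73.4 → 75.9% |
| 4%, 12%, 50% | 0.978 | 1.1% | 0.0238 | 0.0239 / 0.0252 | 66.0 → 67.0% |

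**Weak age effect (3%, 6%, s = 40%).** p = 0.042, V = 0.0402, B = 0.24×0.03² = 0.0002, r = 0.997. Alpha 0.0247, interval 0.3% too wide. With no age effect B = 0 and nothing is lost.

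**Sparseness.** Under the null, with 1000 participants, the five scenarios give 12–20 deaths in the younger stratum and 48–90 in the older. The age-stratified test held alpha at 0.0243–0.0252, so two strata cause no visible sparse-data problem.

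**Missing status counted as failure (Section 9.6.1).** If 3% are missing regardless of age (assumed), each rate becomes 0.03 + 0.97 × rate. At (2%, 15%, 40%) the excess width falls from 3.2% to 2.2%; at (3%, 12%, 40%) from 1.6% to 1.1%.

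**The case against.** The choice is disclosed, reasoned and consistent between the text and Table 5. The analysis is valid. No stated figure is wrong, because none is stated for H2. All of that stands, so this is a matter of efficiency and not an error.

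The size depends on assumptions. The five scenarios use age risk ratios of 3 to 10, and the plan itself expects few deaths. At a ratio of 2 with low mortality the effect nearly vanishes, and counting missing status as failure dilutes it if missingness is unrelated to age. That also stands.

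Age alone still omits two of the three randomization factors, and events in the younger stratum can be few. In the 2% scenarios with 40% aged over 60 there are 300 younger participants per arm. That gives about 6 deaths on placebo and, at a risk ratio of 0.55, about 3 on treatment. This is a fair caution. The simulations nevertheless show alpha held, and the stated reason does not reach a two-level factor.

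A reader might infer from the viral RNA endpoint that the plan contradicts itself. The documents do not support that. The RNA endpoint is exploratory, is estimated without an alpha-controlled test, and its strata are not named. The plan's worry about mortality is the number of deaths, not the number of participants. Nor can the Tier 1 safety rationale be read across, since it concerns events of clinical interest.

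**Conclusion.** The point holds as a minor, optional improvement. The reason given for leaving out strata excludes the 8-cell analysis but not stratification by age alone. If age predicts death, the planned H2 test is slightly conservative. Under the assumed rates (500 per arm, 40–50% over 60, mortality 2–4% and 12–20%), alpha is about 0.020–0.024, the interval about 1–5% too wide, and 1.0–2.5 power points are lost at a risk ratio of 0.55. At 3% versus 6% the loss is negligible. The direction follows from the design whenever age is prognostic; the size cannot be fixed from the documents.

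A reader might infer that error control in Section 9.8 fails because the actual rate is not 0.025. It does not: the rate lies below 0.025, so the claim of strong control stands.

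**What to change.** In Section 9.6.1 and the mortality row and note of Table 5, prespecify the H2 test and estimate as Miettinen and Nurminen stratified by the randomization age group (≤60, >60), and state the stratum weights. Cochran-Mantel-Haenszel weights would be a natural choice; under 1:1 allocation they are essentially proportional to stratum size. Keep the unstratified analysis as supportive.

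The cost is one sentence and one table entry, with no change to data collection, sample size or alpha. It should be settled before Part 2 unblinding, because a later switch would look data-driven. If the sponsor prefers to keep the unstratified test as primary, adding the age-stratified analysis as a prespecified sensitivity analysis would give an age-adjusted estimate but would not recover the power of the confirmatory test.
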